### **5.3.5.8 HIV Testing**

HIV testing will be performed centrally unless prohibited by local regulation, guidelines, or standard practice.

### **5.3.5.9 Fungal Infection and Pulmonary Fibrosis Test**

The (1 to 3)- $\beta$ -D-glucan and KL-6 test will only be performed in regions and/or countries where it is considered the local standard of care at the screening visit. This test should be analyzed locally.

### **5.3.6 Pulmonary Function Testing**

To assess the safety and efficacy of abatacept in IIM subjects with interstitial lung disease (ILD), pulmonary function testing including FEV1, FVC, and DLCO will be performed on all subjects who have clinically active or relevant Interstitial Lung Disease (ILD) or anti-synthetase syndrome at baseline (define in 5.3.7.2). Testing will be obtained at baseline (prior to Day 1), Week 24, Week 52 and Week 76 (or early termination) for subjects with ILD. PFT will be performed and read locally and reviewed by the sites for clinical decision making. No central clinical report will be generated for return to the site.

### **5.3.7 Imaging Assessment for the Study**

Any incidental findings of potential clinical relevance that are not directly associated with the objectives of the protocol should be evaluated and handled by the Study Investigator as per standard medical/clinical judgment. Images will be submitted to the imaging core lab for central analysis as specified below.

#### **5.3.7.1 X-ray Assessment**

A posterior-anterior and lateral chest X-ray, performed during screening, is required for all subjects unless performed within 6 months prior to obtaining written informed consent and documentation of the earlier X-ray is on file. Investigators must ensure that the results of the chest X-ray satisfy criteria for eligibility. The chest X-ray result will be recorded on the appropriate page of the eCRF. This assessment will not be evaluated by a central lab.

#### **5.3.7.2 High-Resolution Computed Tomography (HRCT) Chest**

HRCT of the chest will be obtained to evaluate the extent of lung fibrosis at baseline (prior to Day 1) for subjects who are identified by the investigator as having clinically active or relevant Interstitial Lung Disease (ILD) or anti-synthetase syndrome at baseline (defined as the presence of anti-synthetase autoantibody and at least 2 of the following: ILD, inflammatory myositis or inflammatory polyarthritis).

Subjects with clinically active or relevant ILD will be defined as those who have:

- 1) clinical symptoms of ILD at baseline and/or during the study, or
- 2) worsening ILD, at baseline and/or during the study, as per the treating physician assessment necessitating a treatment change (with documented worsening of at least 2 the following parameters: patient's report of worsening dyspnea, worsening in severity of ground glass opacities (GGO), reticulation or honeycombing or fibrosis on chest HRCT or a decline in the FVC% > 10%) within last 6 months, or
- 3) new onset of ILD (within 3 months of study entry), or
- 4) a clinically relevant decrease in lung function on Pulmonary Function Testing (at the discretion of the investigator)

Subjects with ILD who are evaluated with a HRCT at baseline will also have repeat HRCT performed at Weeks 24, 52, and 76 (or early termination).

In this study, full-chest HRCT should be performed on CT scanners deemed qualified by BMS/assigned imaging core lab. If qualification is not possible, CT scanners approved by local regulations for clinical use can be used to obtain the required images for local review. To ensure comparability, the same scan, equipment, method, and technique used during the baseline HRCT scan should be used for the follow-up HRCT scans (Wk 24, Wk 52, Wk 76, or ET if applicable). At early termination, HRCT conducted only if subject received  $\geq 8$  weeks of study drug and was  $\geq 8$  weeks from previous HRCT. For each subject, HRCT scans will be performed at total lung capacity and residual volume, with no contrast agent (CA) administration, reconstructed every 1 to 1.5 mm, using a low-dose protocol.

The baseline HRCT is to be performed within 28 days prior to the first study drug treatment but after all other eligibility criteria have been met. If necessary, the screening period may be extended by 14 days to accommodate HRCT scheduling.

All HRCT must be read locally and reviewed by site clinical personnel. No central clinical report will be generated for return to the site. For efficacy assessment, HRCT images of baseline, Week 24, Week 52, and Week 76 (or early termination [ET], if applicable) will be processed and analyzed by centralized blinded reader(s). Only HRCTs performed on CT scanners deemed qualified by BMS/assigned imaging core lab will be used for central review. The HRCT analysis will focus on visual and CAD scores for regional lung fibrosis evaluation. Changes in the lung fibrosis scores from the baseline HRCT will be used to evaluate the treatment responses. Detailed HRCT imaging procedures will be defined in an IM101611 imaging manual.

[REDACTED]

Suggestive or typical features of UIP, NSIP or OP on HRCT may suffice for the detection and characterization of ILD and eliminate the need for an invasive and potentially harmful surgical lung biopsy. In IIM-ILD, HRCT parenchymal changes are fairly heterogeneous including basilar and posterior infiltrates, with various patterns that commonly include consolidation rather than

honeycombing in non-septal, linear, plate-like, and sub-pleural patterns. However, it is not uncommon for consolidation to progress to frank fibrosis.

HRCT has been applied in multiple clinical studies of lung fibrosis for drug development, serving as an inclusion criterion, a predictive marker of positive treatment response, and/or efficacy readout. A computer-assisted diagnosis (CAD) score to quantify lung fibrosis as the percentage involvement of reticulation patterns based on texture measures from HRCT has been developed and validated as a measure of quantitative lung fibrosis (QLF) and a potential surrogate imaging marker. CAD scores of QLF have been successfully applied as outcome measurements to test treatment efficacy in ILD trials. Compared with visual assessments, CAD scores have been shown to improve objectivity, sensitivity, and repeatability when measuring quantitative changes in lung features.

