Subjects who discontinue treatment with study medication during the Double-blind Period will complete the Early Termination visit (which is the same visit as Day 169 visit) (See [Table 5.1-2](#)). These subjects must also return on the previously scheduled Double-blind Period Day 169 to complete the Post-Study Drug Efficacy Visit (see [Table 5.1-4](#)). The purpose of this visit is to assess all aspects of disease activity to ascertain the impact of study participation for regulatory review. Subjects must also complete 2 follow-up visits (85 and 169 days after the last dose) during the 24 week post-treatment follow-up period, to perform safety and laboratory assessments (See [Table 5.1-7](#) Post-Treatment Follow-Up Period). This Period begins on the day of the Early Termination visit and applies only to subjects who do not start commercial abatacept therapy.

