**Table 5.1-2: Study Evaluations - Double-Blind Period (IM101611)**

Study Day a	Day 1	Day 29	Day 57	Day 85	Day 113	Day 141	Day 169	
Procedure	Randomization	Wk 4/ Mo 1	Wk 8	Wk 12/ Mo 3 b	Wk 16	Wk 20	Wk 24 / Mo 6 or DB ET c	Notes
DNA for genotyping d	X							Optional collection. See Section 5.6.1.3
Efficacy Assessments								
Physician Global Assessment	X	X	X	X	X	X	X	IMACS Core Component
Subject Global Assessment	X	X	X	X	X	X	X	IMACS Core Component
Manual Muscle Test (MMT-8)	X	X	X	X	X	X	X	IMACS Core Component
Myositis Disease Activity Assessment Tool (MDAAT)	X	X	X	X	X	X	X	IMACS Core Component
Myositis Function Index (FI-2)	X			X			X	
Myositis Damage Index	X						X	
Cutaneous Disease Activity Index (CDASI)	X			X			X	For subjects with DM
████████████████████ ████████████████████							█	████████████████████
Actigraphy data collection		X	X	X	X	X	X	
Imaging Assessments								
HRCT Chest							X	For all subjects with clinically active or relevant ILD or anti-synthetase syndrome. (See Section 5.3.7.2 ).
████████████████████							█	████████████████████

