**Table 5.1-2: Study Evaluations - Double-Blind Period (IM101611)**

Study Day a	Day 1	Day 29	Day 57	Day 85	Day 113	Day 141	Day 169	
Procedure	Randomization	Wk 4/ Mo 1	Wk 8	Wk 12/ Mo 3 b	Wk 16	Wk 20	Wk 24 / Mo 6 or DB ET c	Notes
Outcomes Research Assessments								
HAQ-DI	X	X	X	X	X	X	X	IMACS Core Component
PROMIS Fatigue	X			X			X	
SF-36	X			X			X	

a All visits and procedures must occur within  $\pm 3$  days of the expected visit

b For subjects who are Rescued the visit schedule shall not change

c For subjects who discontinue study drug during this period, the Early Termination visit (DB ET) visit, Post-Study Drug Efficacy visit (Table 5.1-4) and the Post Treatment Follow-Up Period (Table 5.1-7) visits must be done.

[figure not shown]

d If a subject does not consent to the use of their samples for additional research, their samples will be discarded after all protocol-specified testing has been completed (not to exceed 5 years).

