**Table 5.1-4: Post-Study Drug Efficacy Visit (Discontinued Subjects Between Baseline and Wk 24)**

Visit (± 14 days)	169 Days (24 Weeks) Post-Baseline	Notes
Safety Assessments		
Vital Signs	X	
Adverse Event Monitoring	X	
██████████	█	
Pulmonary Function Testing	X	For subjects with ILD (See Section 5.3.6)
Efficacy Assessments		
Physician Global Assessment	X	IMACS Core Component
Subject Global Assessment	X	IMACS Core Component
Manual Muscle Test (MMT-8)	X	IMACS Core Component
Myositis Disease Activity Assessment Tool (MDAAT)	X	IMACS Core Component
Myositis Function Index (FI-2)	X	
Myositis Damage Index	X	
Cutaneous Disease Activity Index (CDASI)	X	
Muscle biopsy (optional - for histopathology and RNA)	X	
Imaging Assessments		
HRCT Chest	X	For subjects with clinically active or relevant ILD or anti-synthetase syndrome. (See Section 5.3.7.2)
██████████	█	████████████████████
Outcomes Research Assessments		
HAQ-DI	X	IMACS Core Component
PROMIS Fatigue	X	
SF-36	X	

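### Protocol text and visit tables disagree on whether a subject with lung disease who stops double-blind drug after 8 weeks has one further HRCT or two, and the 8-week spacing rule does not reach the second

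*Protocol*

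**What the plan says.** The point concerns subjects who had a baseline HRCT because of active or relevant interstitial lung disease or anti-synthetase syndrome, and who stop double-blind drug after at least 8 weeks.

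**The text leans towards one scan.** Protocol 5.3.7.2 says such subjects "will also have repeat HRCT performed at Weeks 24, 52, and 76 (or early termination". For central reading it again treats ET as a substitute: "HRCT images of baseline, Week 24, Week 52, and Week 76 (or early termination [ET], if applicable) will be processed". Section 3.1.2 uses permissive wording for HRCT at Week 24.

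**The tables mark two.** Table 5.1-2 has an HRCT mark in the column shared by Week 24 and double-blind ET, annotated "For all subjects with clinically active or relevant ILD or anti-synthetase syndrome". Table 5.1-4 marks HRCT again at 169 days post-baseline (±14 days), annotated "For subjects with clinically active or relevant ILD or anti-synthetase syndrome". Both rows refer to 5.3.7.2. Footnote c to Table 5.1-2 requires both visits ("For subjects who discontinue study drug during this period, the Early Termination visit (DB ET) visit, Post-Study Drug Efficacy visit"), and 3.1.2 agrees: "These subjects must also return on the previously scheduled Double-blind Period Day 169 to complete the Post-Study Drug Efficacy Visit".

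**The spacing rule covers the ET scan only.** The sentence opens "At early termination, HRCT conducted only if subject received" and sets two conditions: at least 8 weeks of drug, and at least 8 weeks since the previous HRCT. No such condition is attached to the Day 169 scan.

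**The concern.** Sites work from the visit tables. A site that does so will scan at ET and again at Day 169, however close the two fall. A site that treats 5.3.7.2 as governing will scan once. Similar subjects may then be handled differently.

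The protocol has its own view on spacing, at least 8 weeks between scans, but applies it where it does no work in the double-blind period and leaves out the pair that can be close. What is at stake is an avoidable chest CT, acquired at two lung volumes, in a subject with lung disease, and some doubt about which image central reading should take as Week 24.

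**Working it through.** The plan gives no figure on this point, so there is nothing to reproduce. The check is day arithmetic against the plan's own threshold of 8 weeks, or 56 days.

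**Inputs**
- 8-week rule and baseline scan timing: Protocol 5.3.7.2 ("The baseline HRCT is to be performed within 28 days prior to the first study drug treatment").
- Second visit: Day 169 ± 14, so Day 155 to Day 183 (Table 5.1-4).
- ET visit: to be held promptly once dosing has ended (Protocol 5.3).
- Day windows: SAP 8.5, Table 8.5-1.

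**Step 1. Does the look-back block any scheduled double-blind scan?** The baseline scan precedes the first dose. Counting 8 weeks on drug from Day 1, ET is on Day 57 or later, at least 57 − 1 = 56 days after baseline. Anyone who meets the first condition meets the second, so the rule blocks nothing here unless there was an unscheduled scan. It can act in the open-label period, where ET may closely follow the Week 24 scan.

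**Step 2. Gap from the ET scan to the second scan.** Gap = second visit day − ET day.

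| ET day | Visit Day 155 | Visit Day 169 | Visit Day 183 |
|---|---|---|---|
| 57 | 98 | 112 | 126 |
| 99 | 56 | 70 | 84 |
| 100 | 55 | 69 | 83 |
| 113 | 42 | 56 | 70 |
| 114 | 41 | 55 | 69 |
| 127 | 28 | 42 | 56 |
| 128 | 27 | 41 | 55 |
| 141 | 14 | 28 | 42 |

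The gap is never under 56 days for ET up to Day 99. For Days 100 to 127 it depends on the visit date. From Day 128 it is always under 56. With the second visit on Day 169, it is under 56 for ET after Day 113.

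**Step 3. The latest stoppers.** ET on Day 155 or later already lies inside the Table 5.1-4 window. Nothing visible prevents doing both visits that day with one scan. The close pairs that remain have ET between Day 100 and Day 154.

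**Step 4. Do other rules cover the pair?** The overlap rule in 3.5 concerns the follow-up visits 85 and 169 days after the last dose. It mentions neither the ET visit nor HRCT.

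**Step 5. Which image is Week 24?** SAP Table 8.5-1 is introduced for assessments done at every scheduled visit, so applying it to HRCT is an assumption. If it applies, Days 100 to 127 map to Day 113, Days 128 to 155 to Day 141, and Days 156 to 211 to Day 169. An ET image up to Day 155 would therefore not map to Week 24.

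**Step 6. How many subjects?** The documents do not say. Assumptions: stop days spread evenly over 168 days; 20% to 40% with qualifying lung disease; and either 14 early stoppers (twice the 7 missing used in the SAP 7.5.3.2 grid, only as a stand-in) or 5% to 15% of 150, which is 7.5 to 22.5.
- Always close (ET on Days 128 to 154): 27/168 = 0.161.
- Possibly close (ET on Days 100 to 154): 55/168 = 0.327.
- With 14 stoppers: 14 × 0.20 × 0.161 = 0.45 to 14 × 0.40 × 0.327 = 1.8.
- With 7.5 to 22.5 stoppers: 7.5 × 0.20 × 0.161 = 0.24 to 22.5 × 0.40 × 0.327 = 2.9.

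**The case against.** The best answer is that no double scan is established. Both table rows point back to 5.3.7.2, whose wording offers ET as an alternative; 3.1.2 is permissive; and a mandatory visit is not a mandatory scan. This stands to the extent that the finding is a disagreement between text and tables. It does not remove the disagreement, because Table 5.1-4 marks the scan without exception.

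A second answer is that the Day 169 scan is the one worth having. Section 3.5 asks for all efficacy measures at the original Week 24 date, and 3.1.2 gives that visit a regulatory purpose. Dropping it only for late discontinuers removes a fixed-time image from subjects who differ from completers; skipping the ET scan when Day 169 is near would avoid that. This is a fair alternative and a real cost. Against it, the ET scan is already in hand, whereas the later one depends on the subject returning, and 5.3.7.2 already accepts the ET image.

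Third, the scans are low-dose and without contrast, the imaging manual is not available here, and nearby text is blacked out. Either source may settle the matter. That limits the weight of the point, though the tables should still agree with the text.

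**Conclusion.** The point holds as a minor inconsistency. For ET between Day 100 and Day 154, a site that follows the tables can, and from Day 128 will, repeat HRCT within 8 weeks of the ET scan. Under the assumed rates this is about 0 to 3 subjects. The count assumes no unscheduled scans and no withdrawal from follow-up, and the lung-disease share and the discontinuation rates have no source in the documents.

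Three stronger readings are tempting and not supported:
- A reader might infer that the protocol firmly requires both scans. Sections 5.3.7.2 and 3.1.2 point the other way.
- A reader might infer that the very last stoppers are scanned twice within days. From Day 155 the visits can be combined.
- A reader might infer damage to the main results. HRCT is in none of the listed primary or secondary endpoints, and the documents give no dose or harm figure.

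**What to change.** In Protocol 5.3.7.2, with a note on the HRCT row of Table 5.1-4, state that:
- HRCT is not repeated at the Post-Study Drug Efficacy Visit if the ET HRCT was done less than 8 weeks earlier, unless clinically indicated;
- when ET falls on Day 155 or later, one scan serves both visits;
- in these cases the ET image, recorded with its actual study day, is read as the Week 24 (or ET) image.

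Add a matching note to SAP 8.5, since its day ranges would otherwise leave an ET image up to Day 155 outside Week 24. When the gap is 8 weeks or more, both scans are done and the Day 169 scan is the Week 24 image. ET is then no later than 183 − 56 = Day 127, so the two scans cannot both fall in the Day 156 to 211 window.

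The cost is one protocol clarification, one table note and one SAP note. A few late discontinuers lose the fixed-time, off-drug Day 169 image in an exploratory analysis. The primary and secondary analyses are unchanged.

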## **5.4 Efficacy Assessments**

Questionnaires and investigator/subject assessments will be completed prior to study drug administration. If captured on an electronic tablet (ePRO), this device will serve as the source document.

### **5.4.1 Clinical Assessments for the Study**

#### **5.4.1.1 IMACS Definition of Improvement (DOI)**

The IMACS DOI is:

- An improvement of  $\geq 20\%$  from baseline in 3 IMACS core measures, AND
- No more than 2 IMACS core measure scores worsen by  $\geq 25\%$  from baseline, AND
- Manual Muscle Test (MMT-8) may not decrease by  $\geq 25\%$  from baseline

IMACS core measures are:

- Physician Global Assessment of Disease Activity (PGA)
- Patient (Subject) Global Assessment of Disease Activity (SGA)
- Manual Muscle Test (MMT-8)
- Health Assessment Questionnaire-Disability Index (HAQ-DI)
- Muscle Enzyme levels
- Myositis Disease Activity Assessment Tool (MDAAT) Extramuscular Global Activity

The muscle enzymes of interest are creatine kinase (CK), aldolase, AST, ALT, and LDH. To assess the DOI the most abnormal lab value (% above ULN) at baseline will be determined. The subsequent change from baseline for this lab value will be used to determine if the patient has met the DOI at each time point indicated (Table 5.1-2, Table 5.1-3, and Table 5.1-5).

To assess the criteria for worsening, the change from baseline will be determined for all 5 lab values at each time-point indicated (Table 5.1-2, Table 5.1-3, and Table 5.1-5). The lab value with

the greatest percent increase from baseline for each will be used to determine if the patient has met the criteria for worsening respectively ([Section 3.1.5](#)).

Descriptions of the other core measures are below.

#### **5.4.1.2 Assessments Performed by Medical Staff**

The investigator or sub-investigator performing this assessment should have appropriate medical credentials and/or should be individuals with appropriate scientific/medical background who are experienced in performing myositis disease activity assessments. The sub-investigator preferably should be a qualified physician or Doctor of Medicine (MD). Where permitted by local practice and guidelines, a qualified Doctor of Osteopathy (DO), Physician Assistant (PA), or Nurse Practitioner (NP) may perform the Physicians Global Assessment if they have substantial experience assessing patients with IIM. All other non-PGA assessments may be performed by study site personnel that have appropriate relevant clinical or technical training (eg, RN or physical therapist) and are trained to perform the specific IIM study assessments. All individuals that perform study assessments must be recorded in the study file along with their educational background, work experience and training.

##### Physicians Global Assessment of Disease Activity (PGA)

This tool measures the global evaluation by the treating physician of the overall disease activity of the patient at the time of assessment using a 10 cm visual analogue scale that can be performed by the investigator or sub-investigator.

##### Manual Muscle Test (MMT-8)

This tool assesses muscle strength using a 0 - 10 point scale. A set of 7 designated muscles is tested bilaterally plus axial (neck flexor) testing, so that the potential MMT-8 score ranges from 0 - 150. The designated muscles tested will be:

- Neck flexors
- Deltoid middle
- Biceps brachii
- Gluteus maximus
- Gluteus medius
- Quadriceps
- Wrist extensors
- Ankle dorsiflexors

##### Myositis Disease Activity Assessment Tool (MDAAT)

This is a combined tool that captures the physician's assessment of disease activity of various organ systems using (1) a 0-4 scale and (2) a visual analog scale (VAS). It assesses the clinical features of each organ system based upon:

- a) The presence of clinical features or symptoms within the previous 4 weeks that are due to active disease (i.e., use your clinical judgment to determine how active the myositis-associated clinical feature has been within the previous 4 weeks)
- b) The judgment that the feature is due to the myositis disease process (ie, clinical findings known or suspected to be due to another disease process or due to therapy should NOT be considered in this evaluation)
- c) The concept that disease activity is defined as a potentially reversible finding
- d) A clinical, functional, and laboratory assessment for each organ system

The scoring system is based primarily on the physician's intention to treat (Categories A – E). In some cases, a patient may meet the clinical manifestations of a particular category, but the treatment does not match the intention to treat of that particular category; in those cases, the category matching the clinical symptoms should be marked. If more than one clinical symptom is present within a system, and different categories would be scored for each, mark the category that is most severe.

#### Myositis Function Index (FI-2)

The FI-2 is a functional outcome developed for patients with adult polymyositis or dermatomyositis assessing muscle endurance in seven muscle groups. Each muscle group is scored as the number of correctly performed repetitions with 60 or 120 maximal number of repetitions depending on muscle group. The FI-2 is a further development of the original Functional Index (FI) and has been validated as to content and construct validity and intra- and inter-rater reliability. The FI-2 can be performed on both right and left sides requiring a maximum of 33 minutes, or just on the dominant side which takes 21 minutes

